# Introduction

Restrictive eating disorders with pronounced starvation is one of the most acute and life-threatening conditions in child and adolescent psychiatry. The restrictive eating disorders are Anorexia Nervosa, Atypical Anorexia Nervosa and ARFID.

It is crucial that the treatment of these conditions initially focuses on the starvation and achieves a medical stabilization with weight gain for those with an underweight (1). Recent research has shown that weight gain during the first month of treatment gives a better prognosis (2-5). Family-based treatment has the best support in research to achieve weight gain for adolescents with anorexia nervosa (6). Intensive family treatment initially in treatment, which focuses on putting an end to starvation, has proven to be able to achieve sustainable results even after 30 months (7). However, only 26.4% of children and adolescents with an eating disorder in Sweden receive family therapy according to RIKSÄT, the national quality register for eating disorders (8).

The initial treatment for many young patients with an eating disorder is in-patient care, according to RIKSÄT, it is the first registered treatment for 25% of the patients. This underlines the need for a better treatment effort initially. An early-established evidence-based family therapy in outpatient care can prevent the need for hospitalization at a psychiatric clinic, and also improve the prognosis

In order to improve the treatment that patients with restrictive eating disorder and pronounced starvation within Region Skåne receive today, a working group was started in 2017 with the task of drawing up guidelines for these patients who were treated in Child and Adolescent Psychiatry in Skåne. The working group consisted of representatives from the 5 local child psychiatric units that have eating disorder teams, in Kristianstad, Lund, Ystad, Malmö and Helsingborg, as well as the regional unit at Region Skånes Center of Eating Disorders (RSÄ) in Lund.

In order to get a picture of how the initial treatment for new patients with pronounced restrictive eating disorder that comes into treatment at Child and Adolescent Psychiatry works today, the working group collected information from the units within Child and Adolescent Psychiatry in Skåne. The mapping that was done consisted of the 10 most recent patients who came into treatment before November 20, 2016. The information collected was:

- From the initial assessment: Age, waiting time from notification to the first time offered and weight and length.
- After one month: Number of visits during the first month and weight after one month. In total, information about 60 patients was collected.

What the working group found was:

- The age is the same, 15.0 years, at start of treatment.
- How quickly you can offer time for the first visit varies between units. For three units it was around three weeks (19.6, 22.3 and 23.7 days respectively). For the other three units around two weeks (12.1, 15.1 and 15.6 days respectively). The working group has agreed that a waiting period of more than two weeks is not acceptable.
- The number of visits during the first month looks quite similar. An average of 6.2 (between 4.7 and 7.6) is just over a visit a week, which seems reasonable since it means on average more than one visit a week. Some of these visits prove to be visits within day care.

- The weight gain for the whole group was on average 0.98 kg, but some patients had lost weight. The range was -4.2 kg -6.0 kg. Of the patients that had a weight below 90%EBW at start of treatment 23.7% gained 2 kg or more during the first month of treatment.
- How much the patients have gained weight during the first month varied between the different units. The average weight gain varied between 0.1 kg and 1.5 kg between the units. It is lower than 2.0 kg, which is the lowest level of weight gain during the first month that international research has proven to be indication of a better prognosis.

# Aim of the project

Based on the data presented above, it became evident that there is a development work to be done regarding mainly three areas:

- 1. To be able to offer faster times to begin treatment.
- 2. Improve the treatment content by implementing the evidence-based treatment model.
- 3. Offer equal care regardless of where you live.

As part of this development work, the working group has drawn up basic guidelines for intensive treatment during the first month, an evidence-based treatment that focuses on helping the patient normalize eating and lifting the starvation. Treatment with a focus on normalizing the eating will of course continue even after the first month. The working group has also specified which patients should be relevant to this treatment program. Below are the guidelines developed by the working group.

# Guidelines for initial treatment of restrictive eating disorders with pronounced starvation

#### **Patients**

ROCKETLAUNCH treatment is applicable only to patients with an eating disorder with pronounced starvation. The patients included in ROCKETLAUNCH treatment are those who meet the weight criterion for anorexia nervosa according to DSM 5:

"Restriction of energy intake relative to requirements, leading to significantly low body weight in the context of age, sex, developmental trajectory, and physical health. Significantly low body weight is defined as a weight that is less than minimally normal or, for children and adolescents, less than that minimally expected."

For adolescents this represents a weight loss of about 85% of expected weight or lower. For prepubertal children this does not apply, since they have a more pronounced physical impact even at a minor weight loss. Previously overweight patients presenting with weightloss, where the current weight is within the range of normal BMI, may be included in the ROCKETLAUNCH. These are patients who meet the criteria for atypical anorexia nervosa according to DSM 5:

"All of the criteria for anorexia nervosa are met, except that despite significant weight loss, the individual's weight is within or above the normal range".

Also relevant for ROCKETLAUNCH treatment are patients with Avoidant/Restrictive Food Intake Disorder (ARFID), meeting the following DSM-5 criteria:

"Persistent inability to adequately meet the body's needs for nutrients and energy" and:

"Significant weight loss (or failure to achieve expected weight gain or faltering growth in children)"

and/or:

"Significant nutritional deficiency".

The factor which decides if a patient should be included for ROCKETLAUNCH treatment is when pronounced starvation effects are seen at the physical examination, as outlined in the manual.

ROCKETLAUNCH treatment thus pertains to three DSM-5 diagnoses:

- Anorexia Nervosa
- Atypical Anorexia Nervosa
- Avoidant/Restrictive Food Intake Disorder

#### First assessment:

Whenever a young person diagnosed with an eating disorder is suspected to suffer from starvation, an assessment shall be offered promptly, normally at the latest within fourteen days. If significant cardiac symptoms are reported, assessment must be made within a few days. The treating service should be prepared to offer at least 1-2 visits a week directly at treatment start. The assessment includes the following:

- A medical assessment including a physical examination and blood tests (see national guidelines for relevant tests). An ECG should be requested in case of pronounced bradycardia. The assessment should focus on whether the patient suffers from pronounced starvation (see manual).
- Detailed background history including:
  - o eating habits, including developmental trajectory
  - o physical activity
  - o the eating disorder's impact on family and siblings
  - o parent's efforts to help their child
- Physiotherapy assessment is desirable, to assess issues pertaining to body image and excessive exercise
- Basic medical history, screening for any co-morbidity

Based on the assessment, one should primarily determine whether the patient is in starvation and ROCKETLAUNCH is applicable. If so, treatment begins instantly.

# Treatment during the first month.

The treatment focusses with high intensity on medical stabilization and weight gain from the first visit. The goal of the treatment during the first month is a weight gain of at least 2 kg (exception made for atypical anorexia nervosa with a normal or high weight - where the goal is to achieve medical stabilization).

- The treatment always begins at the first visit. Both parents receive "parental allowance for a seriously ill child".
- The patient is put on sick-leave from school. It is important to reconsider this decision at every visit to minimize the time the patient is excluded from their natural social context. As soon as possible a gradual return to school should be instigated.
- At the first visit the clinician must clarify that the patient is suffering from a serious, life threatening condition, far too severe to be managed by the young person him- or herself. Then, the clinician has to charge the parents with the full responsibility for what their child should eat and to support all the meals.
- The treatment should focus on helping the parents to support each other with the difficult task of helping their child to eat.
- Parents should, if necessary, limit excessive physical activity.
- Following the first visit, a maximum of one week should pass until the second visit.
- Physical assessments should be done at least weekly.

- If the patient has lost weight at the second visit, a family meal shall be scheduled within a few days.
- If the patient has not gained weight at the third visit, a second family meal is scheduled.
- If the patient has not reached the target weight gain during the first month, the Regional Eating Disorder Service (RSÄ) may be contacted for a case discussion.

Family meals may be arranged in day care settings, at home visits or at the outpatient clinic. The crucial element in the family meal is to help the parents to be more able support their ill child emotionally and help the child to eat food such as the parents believe their son or daughter needs. For guidelines on implementing the family meal, please see the manual.

# Standardized protocols and treatment manuals

Within the ROCKETLAUNCH project some standardized protocols and manuals have been developed:

- 1. Medical inclusion criteria: A manual for medical inclusion criteria has been prepared. There, it has been clearly specified what it means to be in a pronounced starvation, and how to determine how pronounced the starvation is based on the results of the assessment. It is on the basis of this assessment that one can decide whether the patient should be included in a ROCKETLAUNCH treatment.
- 2. Family therapy in case of restrictive eating disorder with pronounced starvation. First month. A manual in Swedish for the family therapeutic treatment based on the manuals used in the international research that showed that the best treatment method for restrictive eating disorders with severe starvation is family therapy (9,10). The manual describes how family therapy is carried out in the standardized care process, the guidelines outlines the central moments.
- 3. Family meal. A manual in Swedish for how to carry out a common family meal based on the manuals used in international research (9, 10).
- 4. Treatment course, somatic values. A standardized protocol that will be used regularly during the family sessions in order to communicate clearly how the somatic condition changes during treatment.
- 5. EBW%. When assessing underweight in children and adolescents with restrictive eating disorders, it is recommended to use the weight percentage calculated on the BMI value (11). In the project, the investigators have prepared a guide for how this calculation is made, where normal values for different ages are stated. This protocol is a support for the somatic assessment.
- 6. Blood Pressure. A compilation of blood pressure for different ages and also in relation to length, based on Swedish normal value (12). In support of the somatic assessment.
- 7. Pulse. A compilation of normal heart rate for different ages, based on a systematic review of current research (13).

# The importance of the project

The primary part of the project is to improve the prognosis for young newly diagnosed patients with severe restrictive eating disorders, primarily anorexia nervosa, and to reduce the need for in-patient psychiatric care. To achieve this, the project aims to spread competence and knowledge so that the Child and Adolescent Psychiatry services can offer equal care regardless of where you live. According to the national quality register RIKSÄT, only 26.4% of children and young people with eating disorders in Sweden receive the evidence-based family therapy. In addition, 25% are admitted to in-patient care as the first treatment intervention. There is a need to work more intensively to increase the accessibility of the

treatment that is most effective and to prevent those who suffer from restrictive eating disorders has to be long times in hospitals.

# Implementation Preparation

Before the project starts, the investigators intend to make an employee survey. The purpose of the survey is to provide each clinic with a basis for planning and creating good conditions for the implementation of ROCKETLAUNCH. In the previous research (14), the areas that are affected in the survey have proved to be important for how well one can succeed in implementing new methods and way of working. In previous implementation within Child and Adolescent Psychiatry nationally within the framework of the so-called "Deplyftet", where national guidelines for the treatment of depression were implemented, an employee survey was used to identify impeding and favorable factors. The purpose was that each unit should have knowledge of factors grouped as follows, in order to be able to design its specific implementation plan, factors such as:

- 1. Features of the innovation, the guideline itself and the manuals in this case.
- 2. Features of the user of the guideline, employees.
- 3. Characteristics of the target group, the patients.
- 4. Properties in the social environment and the organization.
- 5. Features in the system, economy and administration
- 6. How close to what is described in the guideline is the way of working today on the unit?

# Participants in the project

The project cover the Southern Healthcare Region in Sweden, and the eating disorder units in Skåne, Halland and Blekinge participate in the project. In addition, AnorexiBulimiCenter in Kalmar and Västervik are also involved in the project. This means that all patients with severe restrictive eating disorders in Skåne, Halland, Blekinge and Kalmar can be expected to participate in the project.

# Education and training

In order for the therapists to be able to work according to the guidelines developed, the investigators have to carry out training in the method. The training will be held by [name] and [name]. What is planned so far is:

- 6 training days for all those who work with these patients, who are planned to be implemented during the first year, and will be located in Lund for those who work in Skåne. In Halmstad for those who work in Halland. In Karlskrona for those who work in Blekinge. In Kalmar for those who work in Kalmar County.
- Seminars on the guidelines in smaller groups in the workplaces, which are planned on the basis of how education and competence among the staff looks at the individual workplace.
- Training around family meals with those who work in the same workplace, and co-training with other units so the investigators can know that the patients are offered the same treatment.

### Supervision

Supervision in the clinical work of family therapy in eating disorders will be given continuously during the three years at the various workplaces, mainly by [name].

# Research and evaluation

#### Scientific issues

There are four central issues regarding research and evaluation.

- 1. Are the prerequisites for implementing the guidelines for RAKETSTART optimal? The investigators want to make an assessment of how the clinicians who will carry out the treatment in the project will experience opportunities and difficulties.
- 2. Are the waiting times shortened and are the recommended treatment intensity maintained? An important part of the study is to see if the healthcare system can improve its care for these life-threatening conditions.
- 3. Are the patients improved in the expected extent? The amount of patients that gained 2 kg or more before the project has been 23.7% which means that a greater proportion than that of the intervention group should gain 2 kg or more during the first month of treatment. In a study of FBT 35% of the patients gained 1.8 kg during the first 4 weeks (4), which should be the proportion that the investigators aim for.

One particular issue will be to evaluate the effect of family meals that will only be offered to those patients who do not gain weight as expected. The importance of family meals has been very sparingly evaluated in international research (15).

4. Is the financial burden for family and health care reasonable in relation to the effect? Project ROCKETLAUNCH involves an intensive treatment, which places great demands on both healthcare practitioners and the patient and family. In order to safely justify that this effort is reasonable, the investigators are making a health economic evaluation.

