#### **Data Collection**

# Patient that had been in treatment before ROCKETLAUNCH

Data from the patients who have been in treatment before the project started and meet the medical inclusion criteria will be collected. Data from ten patients at each participating unit on will be collected from the case records.

- The first visit: Age, waiting time from notification to the first time offered and weight and length.
- After one month: Weight. Number of visits to reception and number of visits with family meal. Amount of in-patient care. If the family and patient have been in day care or in-patient care, days of admission will be counted.
- After one year: Weight and length and diagnostic status. Amount of in-patient care. The information about patients before the start of the project will be collected from the same time period at all units.

The data from this early group will be compared with the collected data from the group that will participate in the project.

Weight is regularly monitored in the treatment according to the protocol. These data will include 120 patients from before the project start and approximately 150 patients annually who will enter the project.

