#### The intervention group.

The same data as for the former patients will be collected:

- The first visit: Age, waiting time from notification to the first time offered and weight and length.
- After one month: Weight. Number of visits to reception and number of visits with family meal. Amount of in-patient care. If the family and patient have been in day care or in-patient care, days of admission will be counted.
- After one year: Weight and length and diagnostic status. Amount of in-patient care. The course of the eating disorder is primarily intended to be followed via the national quality register "RIKSÄT", and the additional modules that will be there. The supplement to RIKSÄT is called the FEDiCS (Feeding and Eating Disorder Clinical Support System). What is included is:

EDDA Standardized diagnostic interview based on DSM 5, which is making the interviewer able to make an eating disorder diagnosis. It can be used from the age of 12. (Prepared by RIKSÄT).

MINI kid (16). A diagnostic interview on other psychiatric conditions.

EDE-Q (Eating Disorder Examination - questionnaire) (17). A self-assessment form for eating disorder symptoms. For patients from the age of 12.

PSR (Psychiatric Status Rating Scale) (18). Clinical assessment of the severity of the eating disorder and if the eating disorder is in remission. Rating is made by the interviewer.

RCADS-C (Revised Children's Anxiety and Depression Scale and Subscales) (19, 20). A self-

rating questionnaire which is a screening for symptoms of anxiety, obsession, compulsion and depression. For patients from the age of 12 years.

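### First-month visit totals cannot show whether the recommended visit timing was kept, and they may shift when admissions fall

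*Protocol*

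**What the plan says.** Question 2 under Scientific issues has two halves: "Are the waiting times shortened and are the recommended treatment intensity maintained". The Outcome section names frequency of treatment sessions as a main outcome variable, beside amount of in-patient care, and compares both with patients treated before the project.

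The guideline sections express intensity mainly as timing:
- First assessment: "The treating service should be prepared to offer at least 1-2 visits a week directly at treatment start".
- Treatment during the first month: "Following the first visit, a maximum of one week should pass until the second visit". The same list asks for physical assessments at least weekly.

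What is collected is a total at one month. For the earlier patients it is "Number of visits to reception and number of visits with family meal". The intervention group has the same items: "Number of visits to reception and number of visits with family meal. Amount of in-patient care". Days in day care or in-patient care are counted for the same month in both groups. Visit dates are not listed for either group.

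The Introduction gives the pre-project level: "An average of 6.2 (between 4.7 and 7.6) is just over a visit a week". It adds a caveat: "Some of these visits prove to be visits within day care".

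**The concern.** The measure and the question do not match. The guideline asks when patients are seen, while the data item records how often they were seen over a month. Two patients with equal totals can differ on every timing rule. The item list governs a case-record extraction for 120 earlier patients, so whatever is not extracted cannot be analysed later.

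The total may also be tied to another main outcome. The project aims to reduce in-patient care. If a patient on a ward makes no counted visits, fewer admissions leave more days in which visits can happen. The count then rises although out-patients are seen no more often, and a before-after gain in frequency could partly restate the change in admissions.

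**Working it through.** **1. The protocol's own figure.** Visits per week = monthly count ÷ (days in month ÷ 7). The protocol does not fix the length of the month, so three lengths are shown.

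| Days in month | 4.7 visits | 6.2 visits | 7.6 visits | 1 to 2 a week as a monthly count |
|---|---|---|---|---|
| 28 | 1.18 | 1.55 | 1.90 | 4.0 to 8.0 |
| 30 | 1.10 | 1.45 | 1.77 | 4.29 to 8.57 |
| 30.44 | 1.08 | 1.43 | 1.75 | 4.35 to 8.70 |

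The Introduction's statement that the average exceeds one visit a week is reproduced.

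**2. Timing against totals.** Take two constructed patients with six visits each, close to the mean of 6.2, counting the first visit as day 0:
- Patient A is seen on days 0, 5, 10, 15, 20 and 25. The second visit is within a week, and each of the four weeks has a visit.
- Patient B is seen on days 0, 15, 18, 21, 24 and 27. The second visit comes after 15 days, and days 7 to 13 have none.

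Both enter the data as 6. The total cannot separate them, and dividing it by weeks or by out-patient days does not help. Only dates do.

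**3. Sensitivity to admissions.** Assume no counted visits while admitted and a constant rate r per out-patient day. With share admitted a and L days admitted in a 30-day month:

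mean count = r × (30 − a × L)

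Calibrate r so that the mean is 6.2 at a = 25%, then let a fall to 10%. The new mean is 6.2 × (30 − 0.10 L) ÷ (30 − 0.25 L).

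| L (days) | Out-patient days before | Out-patient days after | New mean | Change |
|---|---|---|---|---|
| 7 | 28.25 | 29.3 | 6.43 | +4% |
| 14 | 26.5 | 28.6 | 6.69 | +8% |
| 21 | 24.75 | 27.9 | 6.99 | +13% |
| 30 | 22.5 | 27.0 | 7.44 | +20% |

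Visits per out-patient day are unchanged in every row, by construction.

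The 25% echoes the national register figure for in-patient care as first treatment. That is not the first-month admission share at these clinics. The 10% and the lengths of stay have no source in the protocol.

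**4. Means against patients.** A unit mean inside the recommended range does not place each patient there. If counts were Poisson (an assumption), 13% of patients at a mean of 6.2 would have fewer than four visits, and 31% at a mean of 4.7.

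**The case against.** The strongest objection is that the denominator is already in hand. Admitted days are collected for the same month in both groups, and dividing one recorded variable by another is commonly left to the SAP, which is not shown. In-patient care is also reported as an outcome, so a move from ward to clinic would be visible. This stands for the admissions effect, which can be adjusted for. It does not reach timing, because the data items themselves lose the intervals.

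Second, the rise with fewer admissions is an inference. No section says that ward contacts go uncounted, and the earlier count included some day-care visits. The admission inputs are assumed, and the 14-day case moves the mean by 0.49 visit against a between-unit range of 2.9 (7.6 − 4.7). This stands, so the figures are illustrations only.

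Third, the Outcome section evaluates adherence separately, and therapists complete a fidelity questionnaire for each family. A standardized somatic protocol is also used in sessions. But the questionnaire follows the therapy manuals, neither source is listed for the earlier patients, and visit dates are not named as research data.

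Fourth, the second-visit rule belongs to the new guideline, so earlier patients cannot be said to have breached it. That is fair: for them the indicator would be a baseline, not a test of compliance.

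Fifth, a rate per out-patient week is undefined for a patient admitted all month and unstable for one with few out-patient days. This also stands and has to be handled in the fix.

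**Conclusion.** The point holds for the intensity half of question 2. A first-month total does not show whether the timing rules were kept, and this needs no numerical assumption. The dependence on admissions is conditional: +4% to +20% if ward patients make no counted visits and the assumed fall in admissions applies.

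A reader might infer more, in two ways that the protocol does not support:
- **That the measure cannot answer question 2.** Waiting time, the other half, is recorded separately and is untouched. The question asks whether intensity is maintained, so a mean count set against one to two visits a week does give part of the answer.
- **That the recommended level was already met, leaving nothing to show.** Maintenance does not require a rise, so a baseline at the recommended level is no defect. The figures are also unit means from the pre-project mapping ("In total, information about 60 patients was collected"), from six units and with some day-care visits included. The comparison group is 120 patients from 12 clinics who must meet the medical inclusion criteria, and its visit frequency is not given.

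This is a cheap improvement to the data items and the outcome definition, not a failure of the design.

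**What to change.** In Data Collection, for both the earlier patients and the intervention group, record the date of each first-month visit in place of a bare total, and state whether day-care visits count.

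In Outcome, compare sessions per out-patient week (visits divided by days not admitted, times seven) beside the raw count. Report patients admitted for the whole month separately.

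Report two patient-level measures of the protocol's existing timing rules: the share whose second visit came within 7 days, and the share with a visit in every out-patient week. No clinical rule changes.

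The cost is extra extraction from the same case records for the 120 earlier patients. The rate will be unstable for patients with few out-patient days, which is a reason to keep the raw count beside it.

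### Scientific question 3 presents 23.7% as the 2 kg rate of all earlier patients, but the Introduction reports it only for those below 90% of expected body weight

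*Protocol*

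**What the plan says.** The figure comes from a mapping described in the Introduction: "The mapping that was done consisted of the 10 most recent patients who came into treatment before November 20, 2016", done at six units. The size is given as "In total, information about 60 patients was collected". The 2 kg result is reported for a subset: "Of the patients that had a weight below 90%EBW at start of treatment 23.7% gained 2 kg or more during the first month". For all mapped patients the text gives only a mean and a range (-4.2 to 6.0 kg): "The weight gain for the whole group was on average 0.98 kg, but some patients had lost weight".

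Scientific issues, item 3, then states "The amount of patients that gained 2 kg or more before the project has been 23.7% which means that a greater proportion than that" is expected of the intervention group. The 90% EBW restriction is gone. The same item adds an aim of 35%, taken from a study of family-based treatment in which that share gained 1.8 kg in four weeks.

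On who enters, the Patients section offers a guide for the anorexia nervosa weight criterion: "For adolescents this represents a weight loss of about 85% of expected weight or lower". It says this guide does not hold for prepubertal children, and it also admits others: "Previously overweight patients presenting with weightloss, where the current weight is within the range of normal BMI, may be included in the ROCKETLAUNCH". Patients with ARFID are eligible too. The deciding factor is signs of pronounced starvation at physical examination. The Participants section repeats the three diagnoses and sets no EBW limit. The section on treatment during the first month sets the 2 kg goal with an "exception made for atypical anorexia nervosa with a normal or high weight".

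**The concern.** Question 3 asks whether patients improve as much as expected, and 23.7% and 35% are the only figures that define that expectation. A reader of item 3 would take the share of the whole intervention group gaining 2 kg and ask whether it exceeds 23.7%. That figure was never reported for a whole group. Patients at or above 90% EBW were left out of it but can be in the intervention group, and their chance of gaining 2 kg may differ in either direction.

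Part of that group, atypical anorexia nervosa at normal or high weight, is exempt from the 2 kg goal, yet item 3 does not mention the exemption. The intervention group could therefore appear to pass or miss the benchmark because of its mix of starting weights and not because of the treatment.

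**Working it through.** **Inputs.** From the Introduction: 23.7%, 60 mapped patients, mean gain 0.98 kg, range -4.2 to 6.0 kg. From Scientific issues, item 3: the 35% aim. The protocol gives no numerator or denominator for 23.7%, so the figure cannot be reproduced directly.

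**Step 1: which counts fit.** Among all fractions k/n with n no larger than 60, only two round to 23.7%:
- 9/38 = 23.68%
- 14/59 = 23.73%

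No count out of 60 fits: 14/60 = 23.3% and 15/60 = 25.0%. So 23.7% is not the rate in the full 60.

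**Step 2: bounds on the whole-group rate.** Assume a one-month weight for all 60. The 60 - n patients outside the subset may contribute none or all of their number, so the rate lies between k/60 and (k + 60 - n)/60.

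| Subset | Outside subset | Lower bound | Upper bound | Difference from 23.7% |
|---|---|---|---|---|
| 9/38 | 22 | 9/60 = 15.0% | 31/60 = 51.7% | -8.7 to +28.0 points |
| 14/59 | 1 | 14/60 = 23.3% | 15/60 = 25.0% | -0.4 to +1.3 points |

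**Step 3: do the reported mean and range narrow the wide case?** The gains must sum to 0.98 × 60 = 58.8 kg. Let those who reached 2 kg have gains from 2 to 6.0 kg, and the rest from -4.2 to just under 2 kg (1.99 used).
- 9 patients at 2 kg or more: from 9 × 2 - 51 × 4.2 = -196.2 kg to 9 × 6 + 51 × 1.99 = 155.5 kg.
- 31 patients at 2 kg or more: from 31 × 2 - 29 × 4.2 = -59.8 kg to 31 × 6 + 29 × 1.99 = 243.7 kg.

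Both intervals contain 58.8 kg, so neither end of the 15.0% to 51.7% range is excluded.

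**Step 4: precision of the benchmark itself.** The 95% Wilson interval is 13.0% to 39.2% for 9/38 and 14.7% to 36.0% for 14/59. Both contain the 35% aim, so even within its own subset the figure barely separates past performance from the target.

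**The case against.** The strongest reply is that 23.7% decides nothing. It enters no test, sample-size calculation or decision rule in the protocol. The Outcome and Data Collection sections plan a comparison with 120 earlier patients who meet the same medical inclusion criteria, and weight gain is among the outcomes compared. On this view item 3 contains a labelling slip whose source can be found in the Introduction. This stands as far as the planned comparison is concerned: it is intact. It does not remove the error, because item 3 still sets the expected improvement by this number.

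Second, the population gap may be small. The adolescent guide of about 85% of expected weight and the exemption for normal- or high-weight atypical patients together suggest that most patients with a 2 kg goal are below 90% EBW. That is plausible but unquantified. Item 3 does not carry the exemption, and prepubertal or ARFID patients at or above 90% EBW could remain.

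Third, the bounds in the 9/38 case are logical extremes, needing none or all of 22 patients to gain 2 kg. The 60 mapped patients are also not said to have met the trial's medical criteria, so their overall rate would not be an exact comparator either. Both points are fair: the range shows what the text leaves open, not a likely error.

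Finally, whether exempt patients count in the denominator may be settled in a statistical analysis plan that is not at hand. Its absence here is no fault, and the finding does not depend on it.

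**Conclusion.** The concern holds. The protocol reports 23.7% for patients below 90% EBW and later restates it, without that limit, as the pre-project rate the intervention group should exceed. The mismatch is certain from the text; its consequence is not. If the count was 14/59 the error is at most 1.3 points. If it was 9/38 the whole-group rate could differ from 23.7% by anything from -8.7 to +28.0 points. These bounds assume that all 60 mapped patients had a one-month weight. The protocol does not say which case applies, and the share of intervention patients at or above 90% EBW is unknown. The planned comparison with the 120 earlier patients is not invalidated. The point should be fixed because the figure is the stated yardstick of a central question and the correction is almost free.

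**What to change.** In Scientific issues, item 3:
- Label 23.7% as the rate among mapped patients below 90% EBW at start, and give its numerator and denominator.
- Set it beside only those intervention patients below 90% EBW at first visit. EBW% can be derived from the age, weight and length already collected, with the guide listed under Standardized protocols and treatment manuals, item 5.
- State that question 3 is answered by the planned comparison with the pre-project group, with one denominator rule for both groups, and that 23.7% and 35% are context.
- Note that 35% refers to 1.8 kg in four weeks, in a study whose title in the reference list limits it to adolescent anorexia nervosa.
- Reconcile the wording with the exemption in the section on treatment during the first month, or point to the document that settles it.

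The change is to wording; no new data are needed. The cost is a smaller group for the benchmark. As an illustration, assume 300 intervention patients (two years at 150) and 22/60 = 37% at or above 90% EBW. That leaves 300 × 38/60 = 190. The 95% half-width at 35%, 1.96 × √(0.35 × 0.65/n), is then 6.8 points with 190 patients instead of 5.4 with 300.

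The between-group comparison need not be restricted in the same way. For 23.7% against 35% (two-sided 5% test, pooled null variance), restricted power with 76 and 190 patients is 0.43. With all 120 and 300 patients, and an assumed pre-project rate of 5% to 47% at or above 90% EBW, power is 0.27 to 0.35 if those patients show no effect and 0.57 to 0.69 if they show the same 11.3 points. Since that effect is unknown, the whole-group comparison can be kept alongside.
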